Study Protocol

Official Title of the study: Effectiveness and safety of Chinese herbal medicine for hepatitis B virus-related acute-on-chronic liver failure: A multi-center, randomized and controlled trial

NCT number: not yet assigned

Date of the document: June 21, 2018

This prospective, multi-center, parallel, centrally randomized controlled trial was designed in accordance with the Consolidated Standards of Reporting Trials (CONSORT) and Standard Protocol Items: Recommendations for Interventional Trials (SPIRIT) guideline, which is led by the principal investigator from 302 military hospital in Beijing, will be carried out from September 2018 and December 2020 among 16 tertiary academic hospitals in China. Patients with hepatitis B virus (HBV) related Acute-on-chronic liver failure (ACLF) will be randomly allocated to the Chinese herbal medicine (CHM) group or the standard medical treatment (SMT) group in a 1:1 ratio. The last patient will be enrolled before August 2019 to make sure the availability of 48 week's survival status by the end of this study. We will decide whether to expand additional institutions to guarantee adequate enrolments after interim assessment of effective participant numbers around December 2018. Patients in the SMT group will receive the standard medical treatment, and patients in the CHM group will receive rhubarb decoction enema for 1 week and CHM for 8 weeks additionally. All patients will be followed at pre-designed time points after 8 weeks' observational period until August 30, 2020 for the primary outcome and secondary outcomes.

The study is consistent with Good Clinical Practice(GCP) guidelines and has been approved by 302 military hospital ethics review committee (2018007D). Written informed consent is requisite to be signed by the patients or the authorized person under the willingness. The privacy and data of all participants will be protected carefully before, during and after the trial.

Patients will be consented and enrolled by co-principal investigators at each institution and managed by care providers including residents, attending physicians and nurses according to the protocol. Most of the patients will be treated in hospital for 8 weeks so clinicians can supervise the administration of CHM, in addition, the policy of reimbursement filed by the lab results at determined time points will boost the regular follow-up of this study.

Diagnostic criteria

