The diagnosis of HBV-ACLF refers to the guideline of liver failure issued by Chinese Group on the Study of Severe Hepatitis B (COSSH) in 2012. In this guideline, HBV-ACLF was described as acute decompensation of liver function within short time (28 days usually) in patients with previously diagnosed or undiagnosed chronic liver disease, reaching the following obligatory criteria: (1) asthenia combined with obvious symptoms of digestive tract, (2) quick progress of jaundice defined as total bilirubin (TBIL) greater than 10 mg/dl or increase 1mg/dl daily, (3) coagulopathy with prothrombin activity less than or equal to 40% or international normalized ratio (INR) greater or equal to 1.5 except other extrahepatic reasons and another dispensable item of decompensated ascites and/or hepatic encephalopathy. There are three grades classified by the degree of coagulopathy and liver complications.

The TCM syndrome was judged by two qualified senior TCM physicians simultaneously based on the published criteria to decide what CHM will be given, and the discrepancy will be solved by consulting another senior physician.

Inclusion criteria

(1) In-patients with ACLF. (2) Patients with chronic hepatitis B or compensated cirrhosis caused by HBV. (3) Patients who are willing to sign the informed consent. (4) Patients aged from 16 to 65 years old.

Exclusion criteria

(1) Acute liver failure, sub-acute liver failure, or chronic liver failure. (2) ACLF caused by another disease such as autoimmune disorder, drug, alcohol, toxin, parasites other than HBV. (3) Pregnant or lactating women. (4) Primary liver cancer. (5) Combined with other severe systemic diseases or mental disease. (6) Anti-HIV positive or combined with infection of hepatitis A, C, D, E virus or cytomegalovirus, Epstein-Barr virus. (7) Patients participating in other clinical trials three months back. (8) Patients unwilling to cooperate. (9) Poor compliance, unable to guarantee to complete the protocol. (10) Complicated by severe cerebral edema, severe infection, type I hepatorenal syndrome (HRS), and gastrointestinal hemorrhage. (11) Patients allergic to one of the Chinese herbs in this protocol.

Criteria for discontinuing or modifying allocated interventions

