The study will end at once if severe adverse events associated with CHM occurs or sufficient evidence indicates that adding CHM is not superior to the SMT group. Besides, CHM will discontinue and the final status will be censored in the condition of liver transplantation or the onset of liver cancer. Allocated interventions can be changed upon participant's request. All these changes will be recorded and analyzed based on intention-to-treat (ITT).

Intervention

Standard medical treatment

The SMT include a high-calorie diet; nucleoside analogues for HBV DNA-positive patients; sodium restriction, diuretics and paracentesis combined with albumin infusion for ascites; lactulose and L-ornithine aspartate and lactulose for HE and hyper-ammonia; hemostatic treatment for gastrointestinal hemorrhage; antibiotics for infections and renal replacement for HRS and uremic symptoms. CHM formulas, whatever routes of administration, are prohibited in the SMT group.

Chinese herbal medicine formula

There are two kinds of CHM based on traditional Chinese Medicines (TCM) syndromes. The common components of the two CHM formulas include *Artemisiacapillaris* Thunb (30g), *Salvia miltiorrhiza* Bge (30g), *Rhizoma*

Atractylodis Macrocephalae (30g), Rubia cordifolia L (30g), Sieyesbeckiaorientalis L (30g). Additional four components of Paeoniae Radix Rubra (60g), Gardenia jasminoides Ellis (9g), Hedyotis diffusa Willd (30g), Bletilla striata (15g) are involved for excess syndrome, and five other components of Astragalus membranaceus (30g), Radix Pseudostellariae (15g), Radix Aconiti Lateralis Praeparata (10g), Galli Gigeriae Endothelium Corneum (20g), Polygonum cuspidatum Sieb.et Zucc (15g) are involved for deficiency syndrome. All ingredients are manufactured as a Chinese herbal granule in a specific weight ratio to the raw herb (Beijing Kang Rentang Pharmaceutical Co., Ltd, Beijing, China) in accordance with the quality criteria of Chinese pharmacopoeia in 2015. Patients will take one dosage of CHM granule per day for 8 weeks. For patients who cannot take oral medicine can be switched to colon route by the colonic therapy system (IMS-100A produced by Sunny Medical in Beijing China).

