In addition, patients in the CHM group will also receive daily herbal enema of 100 microliter decoction composed by Radix et Rhizoma Rhei Palmati (Dahuang) 30g and Fructus Mume (Wumei) 30g for 7 days expect the following contraindications: (1) severe hemorrhoid, (2) female patients during menstruation, (3) anal stenosis, (4) artificial anal and (5) cardiac disease.

Outcome measurements

Primary outcome

The primary outcome is transplant-free survival at week 12.

Secondary outcomes

Secondary outcomes include (1) transplant-free survival at week 24, (2) the influence on liver function assessed by MELD score (involving levels of serum bilirubin, creatinine, INR and sodium) at week 12, (3) the influence on liver function assessed by Child-Pugh score (involving the serum bilirubin, coagulation function, albumin and the complication of hepatic encephalopathy and ascites) at week 12. (4) quality of life assessed by WHOQOL-BRIEF at week 12 and (5) the incidence of serious complications (including infections, encephalopathy, HRS, and gastrointestinal bleeding) from week 1 to week 24.

Safety outcomes

Primary vital signs, physical examinations, electrocardiogram and some laboratory tests such as routine blood test, urine test, renal function will be assessed before and after treatment to monitor the safety of this study. Furthermore, adverse events are also recorded in a predesigned case report form (CRF) through the whole study period. An independent safety committee will analyze the incidence and severity of adverse events to identify any unexpected adverse events or mortality in the CHM groups.

Other assessed parameters

Epidemiological characteristics, the details of nucleoside/nucleotide analog therapy, family history of liver disease were collected from patient medical record, the level of HBV DNA, endotoxin, and lymphocyte subsets were tested as well as CLIP-C-ACLF score were computed at week 24 and 48. The plasma level of HBV DNA, endotoxin, and cytokines were tested in ADICO clinical laboratories (Shanghai, China) which is blind to the allocation information. Remnant plasma will be stored at -80°C for ancillary studies. Women of childbearing age will undergo pregnancy test for the eligibility.

Sample size

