The proposed -12% superiority margin of 8-week mortality rate was chosen based on our previous results of 30.87% in the SMT group. Considering a power of 0.80 and 10% of attrition rate, 255 subjects are needed for each group to achieve the significance level of 0.05 in assessing the difference between the two groups.

Randomization

The eligible patients will be randomly allocated to the SMT group and CHM group in a 1:1 ratio. The sealed numbers are generated by a computerized random number generator with statistical analysis system (SAS) software by an independent statistician from the center of clinical evaluation in China Academy of Chinese medical sciences (Beijing, China) and are concealed using opaque envelopes.

Trial monitoring

Trial monitoring is assumed by an independent Contract Research Organization so as to verify that: (1) The rights and well-being of human subjects are protected. (2) The reported trial data are accurate, complete, and verifiable from source documents. (3) The conduct of the trial is in compliance with the currently approved protocol/amendment(s), with GCP, and with the applicable regulatory requirement(s). Monitors should be appropriately trained and have the scientific and/or clinical knowledge needed to monitor the trial adequately. A risk-based monitoring strategy is developed in this trial, which includes on-site and centralized monitoring, which is more likely than routine visits to all clinical sites and 100% data verification to ensure subject protection and overall study quality. On-site monitoring is an in-person evaluation carried out by the monitor at the sites at which the clinical investigation is being conducted. Centralized monitoring is a remote evaluation carried out at a location other than the sites at which the clinical investigation is being conducted. Key monitoring processes include subject inclusion process; implementation of the inclusion criteria; source data verification; data integrity, etc.

Data management and Statistical methods

Data entry will be conducted by two independent administrators using online electronic CRF for accuracy and consistency. At the end of the study, the database will be locked and analyzed under the agreement of principal investigator and statistician, who are privileged to access the final trial dataset.

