The randomized subjects who take at least one dose of CHM or SMT constitute the full analysis set (FAS) and those who complete all the visits constitute the per-protocol set (PPS). An efficacy assessment will be analyzed using FAS and PPS based on the principle of ITT. Subjects who have taken the CHM and been evaluated the safety at least once constitute the safety set (SS), which is used for safety evaluation. The statistical analysis will be performed using SAS 9.0 software (SAS Institute, Cary, NC, USA) by independent data management committee who are blind to the interventions.

Comparison of the two groups is conducted for the continuous variables with *t*-test and the categorical variables or rates with the chi-square test. The Kaplan-Meier overall survival curves will be generated and tested by log-rank. Cox proportional hazards regression model will be adopted to determine the prognostic factors associated with transplant-free survival. Multivariate logistic regression analyses will be adopted to explore factors associated with the incidence of liver-related complications. Subgroup analyses will be done based on the diagnostic criteria of Asian Pacific Association for the Study of the Liver (APASL) and European Association for the Study of the Liver (EASL) guideline.

The last observation carried forward approach was used for missing values. The statistical significance is defined as a two-sided $P < 0.05$.

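### The rule on participant-requested changes does not say that the CHM ban in the SMT group prevails, and a per-protocol set defined by visits alone cannot check treatment received as planned (minor)

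*Combined protocol and SAP*

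**What the plan says.** All references are to the combined protocol and SAP.

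- **Section headed "Criteria for discontinuing or modifying allocated interventions":** "Allocated interventions can be changed upon participant's request". No arm, direction or limit is given. The next sentence settles the analysis: "All these changes will be recorded and analyzed based on intention-to-treat (ITT").
- **Standard medical treatment:** "CHM formulas, whatever routes of administration, are prohibited in the SMT group". No exception is given, and there is no reference to the request rule.
- **Data management and Statistical methods:** efficacy is analysed in the full analysis set (FAS, randomised patients with at least one dose) and in the PPS, where "those who complete all the visits constitute the per-protocol set (PPS"). Membership does not depend on treatment received, adherence or use of prohibited CHM.
- **Opening section:** "Most of the patients will be treated in hospital for 8 weeks so clinicians can supervise the administration of CHM". Under Trial monitoring, an independent contract research organisation checks that conduct complies with the approved protocol.

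**The concern.** There are two separate gaps.

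**The request rule.** Taken literally, a change of allocated treatment on request includes moving from SMT to CHM, which the ban forbids. No placebo granule or sham enema is described, so an SMT patient would know their arm and could ask for CHM. A site could read the request sentence as permission. A monitor checking compliance would find both rules in the protocol and no order of precedence. If requests were granted and CHM works, the SMT result would move towards the CHM result in the allocated-arm comparison.

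**The PPS.** A per-protocol analysis is meant to show the comparison among patients treated as planned. This one selects on attendance. An SMT patient who took CHM, or a CHM patient who stopped the granules early, stays in the set under the allocated arm if all visits were completed. For the week-12 secondary outcomes measured at visits (MELD, Child-Pugh, quality of life), agreement between FAS and PPS would say nothing about the influence of departures from treatment.

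**Working it through.** **1. Reading the rules together.** The request sentence is general and the ban is specific and unconditional. The usual reading lets the specific rule limit the general one, which leaves stopping, reducing, or leaving CHM for SMT alone as the permitted changes. The section heading fits that reading. The text does not state it, however, and the opposite reading (the request rule as an exception to the ban) is not excluded.

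**2. Who is in the PPS.**

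| Patient | Completes all visits | In PPS as written |
|---|---|---|
| SMT, took CHM | yes | yes, as SMT |
| CHM, stopped early | yes | yes, as CHM |
| Either arm, treated as planned, died before the last visit | no | no |

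The first two rows are the gap. The third row means that nothing follows from it for survival: read literally, the PPS drops patients who die.

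**3. The plan's sample size (background only).** Inputs from the Sample size section: control 8-week mortality 30.87%, margin 12 points (read as absolute), power 0.80, level 0.05, attrition 10%. A margin-type formula with the control rate in both arms gives

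n = 2 × 0.3087 × 0.6913 × (1.960 + 0.842)² / 0.12² = 232.6, so 233 per arm.

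Allowing for attrition gives 257 (× 1.1) or 259 (÷ 0.9), close to the stated 255. The usual superiority formula for 30.87% against 18.87% gives 203, or 226 after attrition. The point does not depend on which was used.

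**4. Illustrative dilution of the allocated-arm comparison.** Let x be the share of SMT patients who take CHM and receive its full effect. Then SMT rate = 0.3087 − 0.12x, CHM rate = 0.1887 and difference = 0.12(1 − x). With p̄ the mean of the two rates,

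power = Φ{[difference − 1.96 √(2p̄(1 − p̄)/n)] / √([p_S(1 − p_S) + p_C(1 − p_C)]/n)}.

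At x = 0 and n = 229.5 (255 less 10%): p̄ = 0.2487, so (0.12 − 1.96 × 0.04035)/0.03996 = 1.02 and power = 0.847.

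| x | Difference (points) | Power, 229.5 per arm | Power, 255 per arm |
|---|---|---|---|
| 0 | 12.0 | 0.847 | 0.882 |
| 5% | 11.4 | 0.812 | 0.851 |
| 10% | 10.8 | 0.772 | 0.814 |
| 20% | 9.6 | 0.678 | 0.724 |

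Power reaches 0.80 at x = 6.5% (15 patients) with 229.5 per arm and at x = 11.7% (30 patients) with 255. If switchers receive half the effect, the first threshold is 13.1% (30 patients).

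These are 8-week mortality figures; the documents give no week-12 rate. Assuming SMT week-12 death-or-transplant rates of 30.87%, 35% and 40%, with either the 12-point difference or the risk ratio 0.1887/0.3087 = 0.611 kept, the power loss at 229.5 per arm is 0.021 to 0.041 at 5% switching, 0.048 to 0.086 at 10% and 0.122 to 0.184 at 20%. In some of these cases power is below 0.80 with no switching at all (0.776 at 40% with a 12-point difference), so the thresholds above belong to the 8-week figures only.

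**5. Why the PPS rule must cover both arms.** Suppose deaths count in the PPS, CHM has no effect, mortality is 30.87% in both arms of 230, and all SMT switchers survive. Removing a share x of SMT patients, all survivors, gives SMT mortality 0.3087/(1 − x):

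| x | SMT mortality | Shift (points) | Chance of a false result favouring CHM |
|---|---|---|---|
| 0 | 30.87% | 0 | 2.5% |
| 5% | 32.5% | 1.6 | about 6% |
| 10% | 34.3% | 3.4 | about 12% |
| 20% | 38.6% | 7.7 | about 38% |

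This is an upper bound. If switchers have half the average mortality, the shift is about half as large.

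**The case against.** The strongest case against is that the text already answers the main question. The ban has no exception, the request sentence never mentions giving CHM to SMT patients, and the analysis of anyone who changes treatment is stated. Most patients are inpatients for the 8 weeks and compliance is monitored. On this view only a cross-reference is missing. Much of that stands, and it is why the point is minor. What remains is that a monitor has no written rule for a request that was granted, and that neither the ITT sentence nor the monitoring changes who is in the PPS.

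A reader might infer three stronger things that the documents do not support:

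- **That the protocol licenses crossover, or that crossover will occur.** No switching rate is given, and the ban points the other way.
- **That the PPS carries the same dilution as the FAS for transplant-free survival.** Patients who die do not complete all visits, so a literal PPS holds almost no mortality contrast to dilute. The PPS criticism is confined to the week-12 MELD, Child-Pugh and quality-of-life outcomes.
- **That the trial is underpowered because of switching.** The losses depend on an assumed rate, on full effect (an upper bound, since a patient must survive long enough to ask), and on removing 10% of patients. The FAS with last observation carried forward may keep nearly all 255 per arm, where the tolerance is larger.

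It can also be objected that excluding only SMT switchers from the PPS could do more harm than the gap it closes. That is correct, as step 5 shows, and the fix takes account of it.

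**Conclusion.** The point holds as a minor one, in two parts. The request rule conflicts on its face with the CHM ban. The ban most naturally prevails and the allocated-arm analysis is specified, so the defect is a missing statement of precedence. The PPS is defined by attendance alone, so it keeps completing patients in either arm who departed from allocated treatment and cannot serve as an as-planned check on the week-12 MELD, Child-Pugh and quality-of-life outcomes.

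Any dilution in the allocated-arm comparison is towards no difference, so it would not manufacture a benefit for CHM. Its size is unknown. On the plan's 8-week figures, with the 12% read as an absolute difference, power stays at or above 0.80 until full-effect switching reaches about 6.5% (229.5 per arm) or 11.7% (255 per arm). The membership finding for the PPS rests on the text and needs no assumption about rates.

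**What to change.** 1. Replace the request sentence with wording such as: *A participant may at any time ask to stop or reduce the allocated intervention. The prohibition of CHM in the SMT group prevails over any such request during the 8-week treatment period, and any CHM use in that group is recorded as a protocol deviation, with its date and direction.* The 8-week limit matches the CHM course; extending the ban for SMT alone to week 24 would create a rule with no counterpart in the CHM group.
2. Define the PPS by absence of major treatment deviations in both arms, in place of visit completion: CHM use in the SMT group, and early stopping of CHM in the CHM group other than because of death.
3. Keep the allocated-arm ITT/FAS analysis primary and label the PPS as supportive only. Report recorded changes by arm.

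The cost is one amended sentence, one revised set definition and two fields on changes that are already recorded. The PPS becomes slightly smaller and remains open to post-randomisation selection even with a two-arm rule, which is why it must stay supportive. SMT participants lose a little flexibility, although they can still stop or withdraw. Some who are refused CHM may withdraw, which would turn a recorded switch into missing data handled by last observation carried forward.

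### The daily enema volume in the experimental arm is given as 100 microliters (0.1 mL), probably 1000 times too small, and nothing else in the protocol corrects it

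*Combined protocol and SAP*

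**What the plan says.** The protocol's opening overview names two additions to standard treatment: "patients in the CHM group will receive rhubarb decoction enema for 1 week and CHM for 8 weeks additionally". It gives the length of the enema course but no volume.

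The volume appears once, at the end of the section headed Chinese herbal medicine formula: a "daily herbal enema of 100 microliter decoction composed by Radix et Rhizoma Rhei Palmati (Dahuang) 30g and Fructus Mume (Wumei) 30g", given for 7 days, with five listed contraindications.

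The same section has one other colonic instruction. Patients who cannot take the granule by mouth "can be switched to colon route by the colonic therapy system". That concerns the oral formula, not the rhubarb enema, and it gives no volume either.

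**The concern.** One hundred microliters is a tenth of a milliliter, about the size of a couple of drops. It is not a usable enema volume, and it sits beside herb weights totalling 60 g.

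The enema is one of the two things that separate the CHM arm from the control arm, and this sentence is its only dosing text. A site that followed it literally would give essentially no enema. A site that gave a sensible volume would depart from the written protocol. Under Trial monitoring, compliance with the approved protocol is one of the things the monitors verify, so the reference document for that check contains a figure no site can sensibly deliver. The overview plans 16 hospitals and allows for more to be added after an assessment around December 2018. Each would have to work out the intended volume for itself.

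**Working it through.** The plan makes no calculation here, so there is no figure to reproduce. The check is a unit conversion followed by a test of whether the volume fits the herb weights in the same sentence.

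**Inputs from the protocol (Chinese herbal medicine formula)**
- Volume per day: 100 microliters
- Herb: 30 g rhubarb + 30 g mume = 60 g
- Frequency and duration: daily for 7 days

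**Assumptions (the protocol gives neither)**
- Extract yield from the raw herb: 10% to 40%
- Prepared volume, if the enema is a portion of a larger batch: 100 to 300 mL

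**Conversion**
- 100 microliters / 1000 = 0.1 mL per day; 0.1 × 7 = 0.7 mL over the course.
- If milliliters were meant: 100 mL per day; 100 × 7 = 700 mL over the course.
- Ratio: 100 / 0.1 = 1000.

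**Reading A: 0.1 mL is the whole decoction**
- Extract mass: 60 × 0.10 = 6 g to 60 × 0.40 = 24 g.
- Concentration: 6 / 0.1 = 60 g/mL to 24 / 0.1 = 240 g/mL.
- Taking water at 1 g/mL, 0.1 mL weighs 0.1 g. For the extract to weigh no more than that, the yield could not exceed 0.1 / 60 = 0.17%.

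This reading is physically impossible at any yield in the assumed range.

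**Reading B: 0.1 mL is a portion of a larger decoction**
- Made up to 100 mL: 60 × 0.1 / 100 = 0.06 g of herb, or 0.1% of the stated 60 g.
- Made up to 300 mL: 60 × 0.1 / 300 = 0.02 g of herb, or 0.03% of the stated 60 g.

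This reading is possible, but the patient receives almost none of the stated herb, and the 30 g weights no longer describe a dose.

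**Reading C: 100 mL was meant**
- Raw herb: 60 / 100 = 0.6 g per mL.
- Extract: 6 / 100 = 0.06 g/mL to 24 / 100 = 0.24 g/mL.

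The sentence is then coherent. The conclusion is the same wherever in the assumed ranges the true yield and batch volume lie.

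**The case against.** The strongest reply is that this is an obvious slip with little consequence. The herbs, their weights, the daily frequency and the 7 days are all stated and not in dispute, so only the volume is faulty. The patients are in-patients at tertiary academic hospitals, and clinicians supervise the treatment. The chance that anyone would give 0.1 mL is remote. That is fair, and neither harm nor divergence between sites has been shown. But noticing the error does not supply an approved volume. A site that rejects 0.1 mL finds no other figure in the protocol.

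Three smaller points also stand in part:

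- **Monitoring.** The plan is risk-based and its named key processes do not include enema volume. The list is open-ended, so a volume check is possible but not specifically required. What remains is that the compliance reference is wrong.
- **Impossibility.** The figure is physically impossible only if 0.1 mL is the whole decoction. As a portion of a larger batch it is merely useless as an enema. Both readings fail, for different reasons.
- **The factor of 1000.** This assumes the numeral 100 is right and only the unit is wrong. The protocol does not say so.

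**Conclusion.** The concern holds: the enema volume is wrong as written. That 0.1 mL is unworkable follows from the unit conversion and the nature of an enema, and does not depend on the assumed yield or batch volume. The size of the error, a factor of 1000, rests on the inference that 100 mL was meant. That is likely but not documented.

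The text applies to up to 255 patients in the CHM arm, less those with a listed contraindication. It is a drafting error in the description of the experimental treatment and has no bearing on sample size, power or analysis. It should be corrected because it is the only dosing instruction for that component.

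**What to change.** The sponsor should check the intended volume against what is actually prepared, then replace 100 microliters with the confirmed figure: 100 milliliters if that is what the check shows. The correction should go to all sites and to the monitors, so that the delivered dose and the compliance reference agree.

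The cost is one word in the protocol and a notice. The overview states that ethics approval has already been given, so the committee may also need to be notified. The document is dated June 21, 2018 and the trial is due to start in September 2018, which leaves time to do this before the first patient.

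### How transplant enters the survival analyses is not settled, and no analysis clearly counts all deaths, so unequal transplant use between visibly different arms could pass as a CHM effect

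*Combined protocol and SAP*

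**What the plan says.** Under Outcome measurements: "The primary outcome is transplant-free survival at week 12". The protocol does not say which events end transplant-free survival. The only other survival outcome listed is the same measure later: "Secondary outcomes include (1) transplant-free survival at week 24". Death from any cause is not a listed outcome.

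Under Criteria for discontinuing or modifying allocated interventions: "CHM will discontinue and the final status will be censored in the condition of liver transplantation or the onset of liver cancer". This is the only rule on how transplant is handled.

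Under Data management and Statistical methods: "The Kaplan-Meier overall survival curves will be generated and tested by log-rank". The event for that analysis is not defined. The Cox model that follows is tied to the other term: "Cox proportional hazards regression model will be adopted to determine the prognostic factors associated with transplant-free survival".

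Under Safety outcomes, an independent committee reviews adverse events "to identify any unexpected adverse events or mortality in the CHM groups". No between-arm comparison of deaths is described there.

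On visibility of treatment, the opening section says "Most of the patients will be treated in hospital for 8 weeks so clinicians can supervise the administration of CHM". CHM patients receive daily granules and a week of enemas. SMT patients receive neither, and CHM is prohibited for them. No placebo or sham is described, and only the assay laboratory and the data management committee are called blind.

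**The concern.** Death is an objective event. Transplant depends on a decision, and here it is likely to be made where the allocation is known. If patients in one arm are put forward for transplant sooner, or transplant is deferred in the other arm to give the herbs time, the primary comparison can move without any effect of CHM on the disease.

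An analysis of death from any cause, with follow-up continued after transplant, would help a reader judge whether that had happened. The protocol does not clearly provide one. The listed survival outcomes are both transplant-free survival, and the overall survival analysis may or may not fall under the censoring rule. At stake is whether a positive result can be read as fewer deaths or may partly reflect different transplant decisions.

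**Working it through.** **1. How the provisions fit together.**
- In its usual meaning, transplant-free survival ends at death or transplant. The discontinuation section instead censors final status at transplant. Both cannot govern the primary outcome.
- Overall survival usually counts every death. If the censoring rule applies to it, deaths after transplant drop out. The protocol does not say whether the rule applies.
- If censored patients were treated as missing at week 12, the last-observation-carried-forward rule would enter them as alive. The protocol does not say whether they would be.

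Two readings of the primary outcome remain: (A) transplant is a failure; (B) transplant is censored, approximated below as a non-event.

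**2. The plan's own figure.** The Sample size section gives 30.87% 8-week mortality under SMT, a -12% margin, power 0.80, 10% attrition and 255 per group. Two-sided 0.05 is stated under the statistical methods.
- Ordinary superiority, 30.87% vs 18.87%, pooled test: 203 per group; 203/0.90 = 226.
- Both arms at 30.87% with a 12-point margin: (1.960 + 0.842)² × 2 × 0.3087 × 0.6913 / 0.12² = 232.6, so 233; 233/0.90 = 259.

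The second form comes close to 255 but does not match it exactly. This is a separate matter; I take 255 as given, and 229 as the number left after 10% attrition (0.90 × 255 = 229.5).

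**3. Effect of a transplant gap when CHM does nothing.** Let g be the gap and n the number per arm. The test is the two-sided 0.05 chi-square, which the plan names for rates.
- Reading A: g more transplants in SMT, all in patients who would otherwise be alive at week 12. Rates are 0.3087 + g (SMT) and 0.3087 (CHM).
- Reading B: g more transplants in CHM, all in patients who would otherwise have died. Rates are 0.3087 (SMT) and 0.3087 − g (CHM).

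P(significant in favour of CHM) = Φ[(g − 1.96·SE₀)/SE₁], with SE₀ = √(2p̄(1−p̄)/n) and SE₁ = √((p₁(1−p₁) + p₂(1−p₂))/n).

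Example, reading A, g = 0.05, n = 255: p̄ = 0.3337, SE₀ = 0.0418, SE₁ = 0.0417, argument −0.764, probability 22.3%. Reading B, same g and n: p̄ = 0.2837, SE₀ = SE₁ = 0.0399, argument −0.709, probability 23.9%.

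| Gap (points) | A, n = 255 | B, n = 255 | A, n = 229 | B, n = 229 |
|---|---|---|---|---|
| 0 | 2.5% | 2.5% | 2.5% | 2.5% |
| 1 | 4.3% | 4.3% | 4.2% | 4.2% |
| 2 | 7.0% | 7.1% | 6.7% | 6.8% |
| 3 | 10.8% | 11.2% | 10.1% | 10.5% |
| 5 | 22.3% | 23.9% | 20.4% | 21.9% |

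Exact binomial calculation agrees closely: reading A gives 10.9% and 22.3% at 3 and 5 points with 255 per arm, and 10.2% and 20.7% with 229. With 255 per arm, gaps of 2, 3 and 5 points are about 5, 8 and 13 patients.

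**The case against.** The strongest reply is that the plan already contains the missing analysis. It uses the term overall survival for the Kaplan-Meier curves and a different term, transplant-free survival, for the Cox model. Overall survival ordinarily counts every death, and the opening section plans 48-week survival status. This stands in part. A reader might infer that no planned analysis counts deaths regardless of transplant; the documents support only that none is clearly specified to do so.

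Three other strong readings also go too far.
- **That transplant definitely counts like death in the primary outcome.** The event is not defined, and the one handling rule says censoring. Under that rule the imbalance that flatters CHM is the opposite one.
- **That treating clinicians who can see the arm decide on transplant.** The visibility of treatment is well supported, although the protocol never says open-label. Who decides on transplant is not stated, so their role is an inference.
- **That deaths and transplants could not be separated afterwards.** They are distinct events, and the protocol says that such changes will be recorded. What is missing is a commitment to compare and report them.

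The illustration is also open to challenge. The gaps are assumed, all extra transplants fall on the patients who matter most, and only the direction favouring CHM is shown. An 8-week mortality rate stands in for week 12, and a censored patient in a log-rank analysis is not quite a non-event. These limits stand, so the table shows sensitivity and is not a forecast.

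**Conclusion.** The concern holds in a limited form. The coding of transplant is contradictory between two sections, the overall survival event is undefined, and nothing in the protocol guards against unequal transplant use between arms that evidently look different to treating clinicians. Under either coding, a modest imbalance could favour CHM without any true effect. For gaps of 2, 3 and 5 points, the 2.5% chance of a significant result for CHM becomes about 7%, 11% and 22–24% with 255 per arm, and about 7%, 10% and 20–22% with 229.

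These sizes rest on assumed gaps, because the protocol gives no transplant rate. If transplant is rare or evenly used, the bias is small. The change is worth making because it is cheap and helps interpret the primary result. The documents do not show that the trial is biased.

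**What to change.** Keep transplant-free survival at week 12 as primary, and:

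1. Reconcile the discontinuation section with the primary outcome by stating once, for every survival analysis, whether transplant is an event or is censored.
2. Define the overall survival event as death from any cause, do not censor vital status at transplant in that analysis, and state that vital-status follow-up continues after transplant.
3. Prespecify one between-arm sensitivity analysis of week-12 death from any cause, with transplant neither censored nor counted as failure.
4. Report the numbers of deaths and of transplants by arm beside the primary result.

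The cost is one extra analysis and two table rows. Survival status to week 48 is already planned. No added patients are needed, because the trial is sized on mortality: for 30.87% vs 18.87%, the formula above gives power of 84.6% with 229 per group and 88.2% with 255.

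There are two drawbacks. A weaker mortality result may temper the claim. Transplant can also itself prevent death, so unequal use affects all-cause mortality too; the added analysis helps interpretation but does not fully isolate the effect of CHM.
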